2.1.8. Timing of Maternal Immunization

In the US, the ACIP states that the optimal timing for Tdap administration is between 27 and 36 weeks gestation although Tdap may be given at any time during pregnancy. [10] Two recent studies support that earlier vaccination may be more beneficial. In Israel, a prospective study that included women in their 20th week of pregnancy or later demonstrated that IgG GMCs to PT were higher in newborn cord sera when women were immunized at 27-30 weeks compared with 31-36 weeks of gestation. [20] Likewise, in a prospective observation cohort study in Geneva, Switzerland, early second-trimester maternal Tdap immunization significantly increased neonatal antibodies compared to later dosing. [21]

In Mali, and elsewhere in Africa, tetanus-containing vaccines are recommended to be given at the first pregnancy encounter. The rationale for this recommendation is that many women in Mali will not present for multiple, regular prenatal visits, as is done in the United States. Thus, the recommendation for first encounter vaccination ensures that a woman receives the vaccine and has adequate time to develop immunity and transfer antibody to her unborn child. Delaying the administration of tetanus-containing vaccines until the third trimester of pregnancy would be a deviation from standard of care, and would likely be unacceptable to the community.

Therefore, second trimester vaccination may be the best option in this trial for consistency with local practices. Any pregnant women who presents in the first trimester and wishes to participate in the study will be asked to return during the second trimester for randomization and receipt of a tetanus-containing vaccine.

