5.1. Subject Inclusion Criteria

Prospective subjects must meet all of the following inclusion criteria to be considered eligible for enrollment:

1. Healthy pregnant woman 18-39 years of age, inclusive.
2. Singleton fetus, with estimated gestational age of 14 0/7 through 26 6/7 weeks gestation, inclusive, on the day of study vaccination.
3. Provide written consent after the nature of the study has been explained according to local regulatory requirements and prior to any study procedures.¹
4. In good health as determined by medical history, targeted physical examination^{2,3}, vital signs^{4,5,6}, and clinical judgment of the investigator.

¹ Prior to obtaining individual informed consent for each subject, the investigators will obtain community consent by discussing the trial with all the appropriate local groups, as necessary, to obtain permission to approach the subjects. Written, informed consent for participation in the trial will be obtained by the investigators from all individual subjects. The consent forms will be written in French, the official language of Mali, and will be translated into Bambara, the most prevalent of the local languages, and recorded on audiotape.

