9.2.4. Grading of Specific Adverse Events in the Pregnant Women and their Infants

Table 8: Maternal and Infant Adverse Events

Maternal Adverse Events (Adverse Events during Pregnancy)				
Parameter	Normal	Grade 1	Grade 2	Grade 3
Pregnancy loss (Pregnancy does not result in a live birth)	None	N/A	N/A	Spontaneous abortion or miscarriage
Spontaneous abortion or miscarriage in the first or second trimester of gestation				
Fetal death at or after 20 weeks of gestation (stillbirth)				
Bleeding (vaginal) during pregnancy prior to the onset of labor	None	Spotting or bleeding less than menses	Bleeding like menses or heavier, no intervention indicated	Profuse bleeding with dizziness or orthostatic hypotension, transfusion indicated
Postpartum hemorrhage	EBL ^c ≤500 cc for vaginal delivery or ≤1000 cc after CS or reported as normal	EBL 501-1000 for vaginal delivery or 1001-1500 for CS or reported as slightly increased	EBL >1000 for vaginal delivery or >1500 for CS, with or without mild dizziness, no transfusion required	Hemorrhage at a level for which transfusion of packed cells or any amount of other blood components is indicated
Postabortal endometritis/salpingitis	None	Low grade fever and uterine tenderness, resolved with oral antibiotics	Moderate symptoms, requiring ≤3 days of parenteral antibiotics	Severe symptoms requiring >3 days of IV antibiotics or development of TOA
Preterm rupture of membranes	None	N/A	Preterm rupture but not resulting in delivery before 37 weeks gestation	Preterm rupture resulting in delivery before 37 weeks gestation

Preterm contractions /labor/delivery^e	None Braxton Hicks contractions (as early as second trimester)	Preterm contractions which resolve without medical intervention	Preterm contractions with cervical change which result in medical intervention but not resulting in preterm delivery	Delivery before 37 weeks gestation
Poor fetal growth If infant is small for gestational age on newborn exam: report as NEONATAL OUTCOME based on birth weight (see below)	At or above 10 th percentile	Fetal growth <10 th percentile but ≥3 rd percentile for gestational age by ultrasound	N/A	Fetal growth <3 rd percentile for gestational age by ultrasound
Hypertension, preeclampsia/eclampsia	None	Pregnancy induced hypertension	Preeclampsia	HELLP syndrome, or eclampsia,

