#### **9.5. Pregnancies**

Every attempt was made to follow subjects to completion of pregnancy to document the outcome, including information regarding any complications with pregnancy and/or delivery. A table summarizing the total pregnancies, number of live births, and number of spontaneous abortions, elective abortions or still births by treatment group will be presented ([Table 75](#)). In addition, a listing of pregnancies and outcomes will be presented ([Listing 18](#), [Listing 19](#), [Listing 20](#), and [Listing 21](#)). A summary of infant size for gestational age at birth by treatment group will be presented in [Table 76](#) and [Figure 233](#).

Pregnancy related adverse events will be collected throughout the study and graded on a scale of 0 (absent), 1 (mild), 2 (moderate) and 3 (severe). Pregnancy related maternal events include pregnancy loss, bleeding during pregnancy or labor, postpartum hemorrhage, postabortal endometritis/salpingitis, preterm rupture of membranes, preterm contractions/labor/delivery, poor fetal growth, hypertension/preeclampsia/eclampsia, chorioamnionitis, postpartum endometritis, gestational diabetes and other pregnancy related AE. Infant events include preterm birth, birth weight, neonatal complications in a term infant, other AE in newborn and congenital abnormality/birth defect ([Table 8](#)).

The proportion of subjects reporting at least one pregnancy related adverse event will be summarized for each pregnancy related adverse event, any maternal symptom, and any infant symptom. The 95% CI will be calculated using Clopper-Pearson methodology from a binomial distribution (SAS Proc Freq with a binomial

(exact) option) will be presented ([Table 77](#) and [Table 78](#)). A Fisher's exact test w the difference in the proportion of subjects reporting a pregnancy related adverse event ([Table 79](#) and [Table 80](#)).

For each pregnancy related event, any maternal event, and any infant event, the maximum severity will be summarized for the maternal and infant Safety populations. The number and percentage of subjects reporting each event will be summarized by the maximum severity and treatment group. ([Table 81](#) and [Table 82](#)). The frequency of pregnancy- and infancy-related adverse events are presented in a bar chart in [Figure 229](#) and [Figure 231](#). The incidence of pregnancy- and infancy-related AEs are presented in [Figure 230](#) and [Figure 232](#).

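### Miscarriage and stillbirth are defined so that they overlap from 20 weeks to the end of the second trimester, which leaves the split in SAP Table 75 and the choice between Listings 20 and 21 to the reporter (minor)

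*Protocol*

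**What the plan says.** Protocol 9.2.4, Table 8, has one graded maternal parameter for fetal loss: "Pregnancy loss (Pregnancy does not result in a live birth". Two descriptions stand under it. One is "Spontaneous abortion or miscarriage in the first or second trimester of gestation" and the other is "Fetal death at or after 20 weeks of gestation (stillbirth". Grades 1 and 2 are marked not applicable, and the Grade 3 cell names only spontaneous abortion or miscarriage. SAP Table 8 repeats this, with both descriptions in one cell and one set of grades.

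The SAP then reports fetal loss in two ways.

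- **As an adverse event.** SAP 9.5 keeps it as one category: "Pregnancy related maternal events include pregnancy loss, bleeding during pregnancy or labor". Tables 77, 79 and 81 each have a single entry for pregnancy loss.
- **As a pregnancy outcome.** SAP 9.5 promises the "number of live births, and number of spontaneous abortions, elective abortions or still births by treatment group will be presented". The shell of Table 75 has three rows: live births, spontaneous abortions, and a combined row for elective abortions or still births. Listing 20 takes still births; Listing 21 takes spontaneous, elective and therapeutic abortions.

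On timing, Protocol 5.1 requires a "Singleton fetus, with estimated gestational age of 14 0/7 through 26 6/7 weeks gestation, inclusive, on the day of study vaccination". Protocol 2.1.8 says that "second trimester vaccination may be the best option in this trial for consistency with local practices". Neither document states in weeks where the second trimester ends.

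Protocol 7.4 attaches a specimen-collection and follow-up rule to stillbirth and does not mention miscarriage.

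**The concern.** One definition has an upper bound in trimesters and the other a lower bound in weeks, and the bounds cross. This is a conflict between two written definitions, not a detail left for later. For a spontaneous loss at 22 weeks, for example, both labels are correct under Table 8 and nothing says which takes precedence.

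The overlap falls within the period under observation. Vaccination starts at 14 0/7 weeks, so every woman vaccinated before 20 weeks passes through the overlap unless her pregnancy has already ended, and women vaccinated from 20 weeks on start inside it.

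Fetal safety is a primary objective, and readers of a maternal vaccine trial will look for miscarriage and stillbirth separately. The protocol's own background (2.1.7) discusses reports of the two outcomes separately. If the separate counts depend on the word a reporter chose, they are unreliable, and with few events expected a single choice is visible.

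**Working it through.** The plan states no figure that rests on these definitions, so there is none to reproduce. The check compares the gestational-age intervals and then follows each label to the displays that use it.

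**1. Intervals.**
- Miscarriage: up to the end of the second trimester (Table 8).
- Stillbirth: from 20 0/7 weeks (Table 8).
- End of the second trimester: not given in weeks. Protocol 2.1.8 speaks of second-trimester vaccination and Protocol 5.1 lets it run through 26 6/7, so the trimester reaches at least 26 6/7. Assumed range for the last day: 26 6/7 to 27 6/7.

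**2. Length of the overlap, counting both end days.**
- Ending at 26 6/7: 7 completed weeks (20 through 26) × 7 days = 49 days.
- Ending at 27 6/7: 8 × 7 = 56 days.

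**3. Position relative to vaccination.**
- Vaccination window, 14 0/7 to 26 6/7: 13 × 7 = 91 days.
- Part of the window inside the overlap: 49/91 = 54%.
- Ages after the start of the window at which only the miscarriage definition applies, 14 0/7 to 19 6/7: 6 × 7 = 42 days.

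These are calendar lengths. They are not shares of expected losses.

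**4. Which displays depend on the label.**

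| Display | How loss is shown | Depends on label? |
|---|---|---|
| SAP Tables 77, 79 | one pregnancy-loss entry | No |
| SAP Table 81 | one pregnancy-loss entry by severity; Grades 1 and 2 not applicable | No |
| SAP Table 75 | spontaneous abortions apart from the combined row for elective abortions or still births | Yes |
| SAP Listings 20 and 21 | still births in one, abortions in the other | Yes |
| Protocol 7.4 | rule stated for stillbirth only | Yes |

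The two listings also hold different details. Listing 20 has columns for cord pH, autopsy and cause; Listing 21 does not. Both have gestational age at the event.

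**5. Size of one relabelled loss in Table 75.** The denominator is the Maternal Safety Population, taken here as the planned 67 and 133.
- Td: 1/67 = 0.0149, or 1.5 percentage points out of one row and into the other.
- BOOSTRIX: 1/133 = 0.0075, or 0.75 points.

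**6. After the fix.** With one stated cut the overlap falls from 49–56 days to 0. Tables 77, 79 and 81 stay as they are; only the Table 75 split and the listing assignment can change.

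**The case against.** The strongest reply is that the overlap does not touch the analysis that carries the primary safety outcome. The primary measure is pregnancy-specific adverse events as set out in Protocol 9.2.4, where loss is one parameter. SAP 9.3 counts each subject once when incidence is calculated, so a loss at 22 weeks is one pregnancy loss under either name. Protocol 11.4.2 lists untoward fetal outcomes individually and, if they exceed 5%, compares them as a pooled proportion. All of this stands.

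Three stronger readings are tempting, and the documents support none of them.

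- *The primary pregnancy-event comparison is altered or double counted.* It is not, for the reasons just given.
- *A stillbirth cannot be graded in Table 81.* The Grade 3 cell is incompletely worded, but the parameter expressly includes fetal death from 20 weeks and Grades 1 and 2 are not applicable. Grade 3 is the only grade available. A footnote to Table 8 also names stillbirth among the complications that meet AE/SAE reporting.
- *Most second-trimester losses will be ambiguous.* The length of the overlap can be turned into a share of follow-up time only by assuming a distribution of gestational age at vaccination. A share of losses would also need the risk of loss by week. The documents give neither.

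It can also be said that Table 75 is descriptive, with intervals but no between-arm test; that gestational age in the listings allows a reader to reclassify; and that assessors are blinded (Protocol 5.3.2), so label choice should not favour an arm. These points limit the harm and make the matter minor. They do not remove it: the table and listings would still report a split that the definitions do not determine.

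**Conclusion.** The definitions are wrong as written, and the point is minor. They overlap for 49 to 56 days, depending on an assumed end of the second trimester between 26 6/7 and 27 6/7 weeks; an overlap exists across that whole range.

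The effect is confined to the by-arm split in SAP Table 75, the assignment to Listing 20 or 21, and the reach of the stillbirth-only rule in Protocol 7.4. Each relabelled loss moves a Table 75 row by 1.5 points (Td) or 0.75 points (BOOSTRIX), assuming the planned arm sizes. The number of such losses cannot be estimated from the documents. The expected harm is an unreliable split, not bias in the pooled comparison.

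Table 75 has a related weakness. Because its shell merges still births with elective abortions, it gives no stillbirth count by arm even when every label is right. Cleaning up the definitions alone would not cure that.

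**What to change.** 1. In both copies of Table 8, make the categories mutually exclusive for reporting by using the 20-week cut already there: spontaneous loss before 20 0/7 weeks is miscarriage, and fetal death at or after 20 0/7 weeks is stillbirth.
2. Name stillbirth beside miscarriage in the Grade 3 cell. This writes down the grade already implied.
3. In the SAP, derive the category from recorded gestational age and use it for Table 75 and Listings 20 and 21. State which recorded age is used, and limit the derivation to spontaneous losses so that elective and therapeutic terminations are not reclassified.
4. Give stillbirths their own row in Table 75, apart from elective abortions.
5. Reconcile Protocol 7.4 with the definitions, so that it is clear which losses its specimen and follow-up rule covers. What that rule should be is for the sponsor and investigators.

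The cost is a short wording change in each copy of Table 8, one derivation and one extra table row in the SAP, and the clarification of Protocol 7.4. The listing shells already include gestational age at the event. Sample size, vaccination and the planned tests do not change.

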3.2. Study Outcome Measures

3.2.1. Primary

Safety and Tolerability:

- Safety in pregnant women: Frequency and severity of study vaccine-related serious adverse events (SAEs), and all SAEs in pregnant women from study vaccination through 6 months postpartum, description and comparison between those receiving BOOSTRIX and Td.
- Safety in pregnant women and fetuses/infants: Frequency and severity of adverse events specific to pregnancy, in pregnant women and their infants (as delineated in [Section 9.2.4](#)), description and comparison between those receiving BOOSTRIX and Td.
- Tolerability in pregnant women: Frequency and severity of solicited injection site and systemic reactogenicity events from study vaccination until 7 days following vaccination (Day 8).
- Tolerability in pregnant women: Frequency and severity of all unsolicited non-serious AEs from day of study vaccination to Day 31, description and comparison between those receiving BOOSTRIX and Td.

- Safety in the infants: Frequency and severity of study vaccine-related serious adverse events, and all SAEs in infants from birth through 6 months of age, description and comparison between infants born to women vaccinated with BOOSTRIX and Td.

Immunogenicity:

- Infant humoral immunity: Geometric Mean Concentration (GMC) of serum IgG antibodies to PT as measured by Enzyme-Linked Immunosorbent Assay (ELISA) at birth between infants born to women vaccinated with BOOSTRIX and Td.

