Severity of Event: AEs will be assessed by the investigator using a protocol-defined grading system (toxicity table included as an appendix). For events not included in the protocol-defined grading system, the following guidelines will be used to quantify severity:

- Mild (Grade 1): Events require minimal or no treatment and do not interfere with the subject's daily activities.
- Moderate (Grade 2): Events result in a low level of inconvenience or concern with therapeutic measures. Moderate events may cause some interference with functioning and daily activities.
- Severe (Grade 3): Events interrupt the subject's daily activities and may require systemic drug therapy or other treatment. Severe events are usually incapacitating.

Changes in the severity of an AE should be documented to allow an assessment of the duration of the event at each level of intensity to be performed. Adverse events characterized as intermittent require documentation of onset and duration of each episode.

Relationship to Study Products: The assessment of the relationship of an AE to the administration of study product is made only by those with the training and authority to make a diagnosis and listed on the Form FDA 1572 as an investigator based on all available information at the time of the completion of the eCRF. Whether the AE is related or not, is not a factor in determining what is or is not reported in this trial. If there is any doubt as to whether a clinical observation is an AE, the event should be reported.

In a clinical trial, the study product must always be suspect. To help assess, the following guidelines are used.

- Related – There is a reasonable possibility that the study product caused the adverse event. Reasonable possibility means that there is evidence to suggest a causal relationship between the study product and the adverse event.
- Not Related – There is not a reasonable possibility that the administration of the study product caused the event.

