Chorioamnionitis	None	Fever (38°C–38.4°C or 100.4°F–100.9°F) with two or more: FHR ^e >160 BPM ^f , maternal HR >120, uterine tenderness between contractions or purulent AF or preterm labor	Same as Grade 1 plus fever 38.5°C–40°C or 101°F–104°F	Criteria for Grade 2 plus fetal distress or fever >40°C or 104°F
Postpartum endometritis	None	Low grade fever and uterine tenderness, resolved with oral antibiotics	Moderate symptoms, treated by ≤3 days of parenteral antibiotics	Severe symptoms treated with >3 days of IV antibiotics, addition of heparin, or operative intervention
Gestational diabetes mellitus	N/A	New onset controlled by diet	New onset with initiation of medical therapy	Uncontrolled despite treatment modification
Clinical AE, pregnancy-related, NOT identified elsewhere in this AE Grading Table	None	Symptoms causing no or minimal interference with usual social & functional activities	Symptoms causing greater than minimal interference with usual social & functional activities	Symptoms causing inability to perform usual social & functional activities

Mode of delivery^f (normal spontaneous vaginal delivery, induced delivery, assisted vaginal delivery, Caesarean Section)	Not reported as AE/SAE. Mode of delivery is a procedure and should not be reported or graded as an AE/SAE. The reason for selecting the mode of delivery (for example: Caesarean Section for severe preeclampsia) should be reported and graded as appropriate.
--	---

**Infant Adverse Events
(Neonatal and Infant Events)**

Parameter	Normal	Grade 1	Grade 2	Grade 3
Preterm birth^g	Born after 36 6/7 weeks gestation	Late preterm: 34 to 36 6/7 weeks gestation	Early preterm: 32 to 33 6/7 weeks gestation	Very or extremely preterm: ≤ 31 6/7 weeks gestation
Birth weight (grams)^g (Small, appropriate, large for gestational age)	Birth weight ≥2500		Low birth weight: 1501-2500	Very low birth weight ≤1500
Report separately poor fetal growth (as above)				
Neonatal complications in a term infant	Normal term infant discharged home with mother after uncomplicated delivery and nursery course	Transient signs and symptoms requiring no interventionⁱ , and resolved spontaneously ^h	Signs/symptoms requiring interventionⁱ but discharged home with mother (± 2 days) , or close to it	Required NICU for more than 1 week, and/or interventions (including surgery) leading to prolonged hospitalization (report SAE) ^j

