11.2.3. Sample Size

The study is planned to enroll 200 pregnant women (133 BOOSTRIX, 67 Td).

This will be one of the first studies of maternal Tdap vaccination in an African, low resource setting, and where infants received whole cell, rather than acellular pertussis vaccinations. Thus, this study is intended to obtain preliminary estimates of immune response in this setting; it is not designed to test a specific null hypothesis. The tables below describe the power to detect safety events and the precision available for estimating immune response for the planned sample size. [Table 9](#) indicates the probability of observing one or more safety event, such as solicited injection site or systemic symptom, or an unsolicited adverse event of a particular type within a treatment arm.

Table 9: Power (%) to Detect Safety Events

Event Frequency	N = 133	N = 67
≥0.01% Rare	1.3	<1
≥0.1% Uncommon	12.5	6.5
≥1% Common	73.7	49.0
≥10% Very Common	100.0	99.9

In addition to safety, as a co-primary objective, the study will assess serum PT antibody at birth among infants whose mothers received a single dose of BOOSTRIX, and as secondary and exploratory objectives, the study will assess maternal and infant humoral response to all vaccine antigens. Immune response will be measured by ELISA. [Table 10](#) presents the precision (95% CI) available for estimating GMC of ELISA titers against the vaccine component using assumptions for GMC and standard deviation (SD) for maternal and infant response to Tdap from Munoz et al. [13] and infant response post third dose of primary DTwP vaccine series from Ladhani et al. [34]

Table 10: Precision for Estimating GMC of ELISA Antibody Response

GMC	SD (log-scale)	95% CI Estimate		
		N = 133	N=67	
Maternal ELISA Antibodies at Delivery following maternal Tdap				
PT	51	0.90	43.7	59.5
FHA	184.8	0.73	163.1	209.3
PRN	184.5	1.45	143.8	236.7
FIM	1485.7	1.17	1214.8	1817.0
Infant ELISA Antibodies at Birth following maternal Tdap				
PT	68.8	0.78	60.2	78.7
FHA	234.2	0.67	208.7	262.8
PRN	219	1.38	172.9	277.4
FIM	1867	1.22	1514.7	2301.3
Infant Response post 3rd Dose DTwP following maternal Tdap				
PT	28.8	0.68	25.6	32.3
FHA	25.5	0.60	23.0	28.3
FIM	113.9	0.81	99.1	130.9
Infant Response post 3rd Dose DTwP (no maternal vaccination)				
PT	43.2	0.65	38.6	48.3
FHA	41.1	0.66	36.7	46.1
FIM	224.9	0.97	190.2	265.9
			177.2	285.4

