**Table 18: Summary of Infant Continuous Demographic and Baseline Characteristics by Treatment Group**

Variable	Statistic	BOOSTRIX (N=X)	Td (N=X)	All Subjects (N=X)
Gestational Age at Delivery (days)	Mean	xx.x	xx.x	xx.x
	Standard Deviation	xx.x	xx.x	xx.x
	Median	xx.x	xx.x	xx.x
	Minimum	xx	xx	xx
	Maximum	xx	xx	xx
Birth Weight (kg)	Mean			
	Standard Deviation			
	Median			
	Minimum			
	Maximum			
Length (cm) at Birth	Mean			
	Standard Deviation			
	Median			
	Minimum			
	Maximum			
Head Circumference (cm) at Birth	Mean			
	Standard Deviation			
	Median			
	Minimum			
	Maximum			

Note: N= Number of subjects in the Infant Safety Population

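### A birth weight of exactly 2500 g is both Normal and Grade 2 in Protocol Table 8, so whether that infant has an adverse event is undefined

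*Protocol*

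**What the plan says.** Protocol Section 9.2.4, Table 8, grades infant birth weight in grams. Normal is "Birth weight ≥2500", Grade 2 is "Low birth weight: 1501-2500" and Grade 3 is "Very low birth weight ≤1500"; there is no Grade 1. Footnote g to that table deals only with reporting preterm birth and low birth weight separately. Protocol Section 9.1 lists low birth weight as an infant event without a cut-off.

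Grading is done at the site from the protocol's table. Protocol Section 9.2.1 states: "AEs will be assessed by the investigator using a protocol-defined grading system".

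SAP Table 8 carries over the same Grade 2 and Grade 3 ranges but has no Normal column. SAP Section 9.5 makes birth weight an analysed event: "Infant events include preterm birth, birth weight, neonatal complications in a term infant, other AE in newborn and congenital abnormality/birth defect". These events get exact confidence intervals (Table 78), Fisher's exact test between arms (Table 80) and a maximum-severity summary that includes a None row (Table 82). They also feed the infancy-related rows of Table 46.

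The Section 9.2.4 events are a primary safety outcome in Protocol Section 3.2.1: "Frequency and severity of adverse events specific to pregnancy, in pregnant women and their infants", described and compared between arms.

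**The concern.** Two cells in one row contradict each other at a single value. The disagreement is not between two grades but between no event and a Grade 2 event. Two investigators can both follow Protocol Table 8 to the letter and differ on whether a 2500 g infant has an adverse event at all. The SAP does not settle this: it does not say that its table overrides the protocol's Normal definition, that the category is derived from recorded weight, or what None means for birth weight in Table 82.

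At stake are the low-birth-weight count and, for an infant with no other graded event, the any-infant-event count. If the boundary is left open until the data are seen, someone must choose a classification for part of a primary safety outcome after the fact.

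**Working it through.** The documents state no low-birth-weight rate and no sample-size or power figure that depends on one, so there is no figure of the plan's own to reproduce.

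**Step 1: is 2500 g the only ambiguous value?** Code the protocol's cells as Normal: w ≥ 2500; Grade 2: 1501 ≤ w ≤ 2500; Grade 3: w ≤ 1500. Test every whole gram from 300 to 6000.

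| Weight (g) | Categories met |
|---|---|
| 1500 | Grade 3 |
| 1501 | Grade 2 |
| 2499 | Grade 2 |
| 2500 | Normal and Grade 2 |
| 2501 | Normal |

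Only 2500 g meets two categories, and no weight meets none. The lower boundary in the same row (1500/1501) is clean, and so is the 500/501 split for vaginal delivery in the postpartum hemorrhage row. The overlap therefore looks like a slip rather than a convention of the table.

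**Step 2: effect of one infant.** The planned arms are 133 and 67 women (Protocol Section 11.2.3), each with a singleton pregnancy (inclusion criterion 2). One infant at 2500 g moves the rate by:
- BOOSTRIX: 1/133 = 0.75 percentage points
- Td: 1/67 = 1.49 percentage points
- Overall: 1/200 = 0.50 percentage points

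With fewer infants than planned, each step is slightly larger.

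**Step 3: how many infants could be affected?** The documents give neither the birth-weight distribution nor the recording precision. Assume, for illustration, a normal distribution with mean μ = 3000 to 3200 g and SD 450 g, recorded to the nearest r grams. Then:
- share recorded below 2500 g = Φ((2500 − r/2 − μ)/450)
- share recorded at 2500 g = Φ((2500 + r/2 − μ)/450) − share below
- relative rise in the low-birth-weight rate = share at ÷ share below

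Worked case, r = 100:
- μ = 3000: Φ(−1.2222) = 0.1108 and Φ(−1.0000) = 0.1587. Share at 2500 g = 0.0478; 0.0478/0.1108 = 43%.
- μ = 3200: Φ(−1.6667) = 0.0478 and Φ(−1.4444) = 0.0743. Share at 2500 g = 0.0265; 0.0265/0.0478 = 55%.

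| Recording unit r | Below 2500 g | At 2500 g | Relative rise | Infants at 2500 g per 200 |
|---|---|---|---|---|
| 1 g | 6.0-13.3% | 0.03-0.05% | about 0.4% | about 0.1 or fewer |
| 10 g | 5.9-13.1% | 0.3-0.5% | about 4% | 0.5-1.0 |
| 50 g | 5.4-12.2% | 1.3-2.4% | 20-25% | 2.6-4.8 |
| 100 g | 4.8-11.1% | 2.7-4.8% | 43-55% | 5.3-9.6 |

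The result is governed almost entirely by the recording unit.

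**The case against.** The strongest case on the other side is that this is one value on one row and that the trial's conclusions do not turn on it. Much of that stands.

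- **Precision.** Nothing in either document says that weights are rounded to 50 or 100 g. The protocol row is in grams, and its 1500/1501 split presupposes whole-gram values. SAP Table 18 and Listing 6 report kilograms but do not fix the decimals for birth weight. A reader might infer from the 100 g row that the rate is likely to rise by about half. The documents do not support that: it is the coarsest of four assumed units, and with 10 g recording about one infant in the whole trial is affected.
- **Bias.** A reader might infer that the comparison between arms is distorted. Assessors are blinded (Protocol Section 5.3.2), so there is no reason to expect the boundary to be read differently by arm. What suffers is the absolute rate and the consistency of grading.
- **Decisions.** The trial is described as testing no specific null hypothesis and adjusts for no multiplicity (Protocol Section 11.2.3; SAP Section 6.8), so no success rule depends on Table 80. The halting rule for pregnancy-related events uses Grade 3 (Protocol Section 9.5), whose birth-weight range has no overlap.
- **The SAP table.** A reader might infer that SAP Table 8 deliberately reclassifies 2500 g. It omits the Normal column for every parameter, so this is layout rather than a competing definition.
- **Recoverability.** Birth weight is summarised as a continuous variable and listed per infant, so either count could be rebuilt from Listing 6 if the weights are listed finely enough.

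These points limit the size of the problem; they do not remove it. The grade is assigned at the site from the protocol table, and that table gives two answers.

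**Conclusion.** Wrong as written; minor. Protocol Table 8 assigns 2500 g to two categories, nothing in either document resolves it, and SAP Table 8 repeats one side only. The affected outputs are the birth-weight and any-infant-event rows of SAP Tables 78, 80 and 82 and the infancy-related rows of Table 46, which report part of a primary safety outcome. Sample-size figures are unaffected.

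The overlap itself and the effect of one infant at the planned arm sizes need no assumption about the birth-weight distribution. The relative rise, from about 0.4% to 55%, rests on an assumed normal distribution and an unknown recording unit, and should be read as a range rather than an estimate. The documents do not show which side of the boundary was intended.

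**What to change.** Reconcile the Normal and Grade 2 cells in Protocol Table 8 with each other and with SAP Table 8, so that 2500 g falls in exactly one category. Either choice removes the overlap:
- keep the Normal cell and make Grade 2 read 1501-2499 in both tables; or
- keep the Grade 2 cell and make Normal read >2500 in the protocol, and state the same boundary in the SAP.

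Add a sentence to SAP Section 9.5 saying that the birth-weight category in Tables 46, 78, 80 and 82 is derived from the recorded weight, before any rounding for display, using that single boundary. Stating the recording precision there would let readers judge how much the choice matters.

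Settle both before unblinding. The cost is a small edit to one or two table cells and one or two sentences in the SAP. Birth weight is already collected and listed, so no new data are needed.
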